9.2.3 Adverse Events of Special Interest

The following AESIs have been identified for the study intervention in this study: visual disturbance (including, but not limited to, any loss of vision, vision, double vision, pain in

or around eye [excluding pain in temple area], blind spot or shadow in the visual field, trouble moving eyes, etc.).

The incidence of AESIs will be summarized by SOC and PT and listed in a separate listing.

9.3 Analysis of Laboratory Data

Not applicable.

9.4 Vital Signs

Vital sign is collected at screening including blood pressure (systolic and diastolic; while participant is seated), pulse rate, and temperature. Vital sign will be listed.

9.5 Height and Weight

Height is collected at Screening visit. Weight is collected at Screening, Month 3 in CP for both treatment and control groups and at Month 13 in TP for treatment group. Height and weight at Screening visit will be summarized as baseline characteristics. Weight will be listed.

9.6 Pregnancy Test

Participants with a positive result for the safety population will be listed.

9.7 Injection Site Response

ISRs recorded in participant diaries after each treatment (initial, touch-up, and maintenance). Diary Day is derived as diary date - treatment date + 1 (e.g., the day of treatment is diary Day 1). ISR entry includes diary data and eCRF data on Ongoing ISR page. The maximum severity and ISR duration are based on diary data and eCRF data for the specified treatment (e.g., the maximum severity for touch-up treatment is based on diary data and eCRF data after touch-up treatment.).

Number (%) of participants will be summarized for each treatment by predefined symptoms. The number of participants with ISR entries (diary data and eCRF data) for each treatment is used as the denominator for the calculation of percentages. The ISR analyses are listed in Table 10.

Table 10. Injection Site Response Analyses

Endpoint	Description	Timing	Methodology
ISR severity	Number of participants with ISRs by symptom incidence and categorized by maximum reported severity	Initial, Touch-up, Maintenance	Frequency counts and percentages
ISR duration	Number of participants with ISRs by symptom incidence and categorized by duration. Duration is defined as number of days from first instance of the symptom to the last instance of the symptom within the planned diary period. Duration is derived as date of last ISR - date of first ISR + 1. Duration of any ISR is calculated using the same algorithm regardless of ISR symptom.	Initial, Touch-up, Maintenance	Frequency counts and percentages, continuous descriptive statistics
Ongoing ISR	ISRs recorded on Ongoing ISR page		Listing

If a participant reported more than one "Other" ISR, the participant will be counted once in the summary for that treatment. For "Other" ISR, severity and duration analyses described in Table 10 will be performed. "Other" ISR may be summarized by category when free text categorization is applicable and relevant information is available.

9.8 Procedural Pain

Participant assessment of procedural pain (pain during injection) on an 11-point scale ranging from 0 (no pain) to 10 (worst pain imaginable) after initial, touch-up and maintenance treatment will be summarized. The summary will be performed by treatment group for VT and VMT as described in Table 11.

change represents an improvement, and a negative change represents a worsening. Baseline is the pre-treatment value on or before the most recent treatment.

$$\text{Line change} = 10 \times [\log_{10} (d_{\text{baseline}}/20) - \log_{10} (d_{\text{follow-up}}/20)]$$

where d_{baseline} = denominator of the Snellen equivalent score at baseline,

$d_{\text{follow-up}}$ = denominator of the Snellen equivalent score at follow-up visit

Positive findings in confrontation visual fields assessments (e.g., No is reported for "Is eye full to confrontation?" or Yes is reported for "Is there a change from pre-treatment?"), will be listed.

Positive findings in ocular motility (e.g., No is selected for "Does the eye have full duction and version?" or Yes is reported for "Is there a change from pre-treatment?") will be listed.

[REDACTED]

[REDACTED]

[REDACTED]

Concomitant medications (Section 7.3) and concurrent procedures (coded using MedDRA) will be listed.

10.0 Other Analyses

Not applicable.

[REDACTED]

[REDACTED]

[REDACTED]

[REDACTED]

[REDACTED]

[REDACTED]

[REDACTED]

[REDACTED]

11.1 Data Monitoring Committee

No data monitoring committee is planned for this study.

12.0 Overall Type-I Error Control

All statistical tests will be 2-sided hypothesis tests performed at the 5% level of significance for main effects. All CIs will be 2-sided 95% CIs, unless stated otherwise. A gatekeeping procedure will be used for hypothesis testing of the primary endpoint (ATHS responder) and 2 of the secondary endpoints (FACE-Q Satisfaction with Facial Appearance and FACE-Q Satisfaction with Temples) following a predefined sequence to control the overall Type I error rate at the 0.05 level. The primary hypothesis must be rejected in order to test the FACE-Q Satisfaction with Facial Appearance. Additionally, statistical significance must be established for FACE-Q Satisfaction with Facial Appearance in order to assess the hypothesis for FACE-Q Satisfaction with Temples.

For the secondary effectiveness endpoints of GAIS responder status at Month 3 as assessed by the EI and as assessed by the participant, the 95% CI will be provided for the proportion of responders within each treatment group, where applicable. No multiplicity

adjustments will be made for the 2 GAIS responder rates since these endpoints and associated statistics are intended to be descriptive rather than inferential.

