#### Number of Participants:

Up to 213 participants will be enrolled and screened to achieve 171 randomized (114 treatment group, 57 control group) and 135 evaluable participants (90 treatment group, 45 control group) at the Month 3 primary timepoint.

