8.3.3 Primary Effectiveness Analysis

Primary effectiveness analysis will be performed based on the mITT population. The study intervention will be considered clinically effective if both of these criteria are met:

- The ATHS responder rate for the treatment group is statistically superior to the responder rate for the control group at Month 3
- At least 60% (a point estimate of 60% or greater) of participants treated with VOLUMA XC are ATHS responders at Month 3

For the first criterion, the null and alternate hypotheses are:

$$H_0: P_v = P_c \text{ versus } H_a: P_v \neq P_c$$

where P_v and P_c denote the responder rates for the treatment group at Month 3 after the latest of randomization, initial treatment and touch-up treatment, and control group at Month 3 after randomization, respectively.

If there are no mITT participants with missing scores for the primary effectiveness endpoint, a 2-sided Fisher's exact test with 5% significance level will be used to compare responder rates between treatment and the control group. Otherwise, the methods described in Section 8.3.2 will be applied. If the 2-sided p-value is ≤ 0.05 , which implies that the responder rate between treatment and control is different, and the point estimate of the responder rate for the treatment group is greater than for the control group and is 60% or greater, then treatment will be considered clinically effective. In addition, responder rates and 95% CIs will be calculated for treatment group and control group. No hypothesis testing will be performed for the second criterion.

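### Should the gate to the FACE-Q tests require the 60% responder criterion as well as rejection of the primary null hypothesis?

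*SAP*

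**What the plan says.** SAP 8.3.3 (Primary Effectiveness Analysis) sets a two-part rule: "The study intervention will be considered clinically effective if both of these criteria are met". The parts are statistical superiority of the treatment-group responder rate over control at Month 3, and a treatment-group point estimate of 60% or more. The formal hypothesis belongs to the first part only: "For the first criterion, the null and alternate hypotheses are" Pv = Pc against Pv ≠ Pc. Of the other part it says: "No hypothesis testing will be performed for the second criterion".

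SAP 12.0 (Overall Type-I Error Control) places the primary endpoint and the two FACE-Q scales in a gatekeeping procedure, "following a predefined sequence to control the overall Type I error rate at the 0.05 level". The first gate is "The primary hypothesis must be rejected in order to test the FACE-Q Satisfaction with Facial Appearance"; the second is that "statistical significance must be established for FACE-Q Satisfaction with Facial Appearance in order to assess the hypothesis for FACE-Q Satisfaction with Temples". Section 12.0 does not mention the 60% criterion.

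Under SAP 8.4 each FACE-Q test is a two-sided paired t-test at 5% on the change from baseline within the treatment group.

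**The concern.** The success rule has two conditions and the gate has one. If superiority is shown but the treatment-group rate falls short of 60%, the SAP still sends FACE-Q Satisfaction with Facial Appearance, and possibly then FACE-Q Satisfaction with Temples, to formal testing. A trial that had not met its own effectiveness rule could then report a significant, error-controlled secondary result.

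The usual reading of gatekeeping is that secondary claims are open only once the primary objective has been achieved, so this looks like an oversight. If it were one, the status of the FACE-Q results in that case would be open to argument after the data were seen.

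**Working it through.** **1. What the gate refers to.** SAP 8.3.3 contains one null hypothesis, Pv = Pc, attached to the first criterion, and it excludes the second from testing. An untested point-estimate threshold cannot be rejected, so the primary hypothesis in SAP 12.0 has a single referent. The two sections answer different questions: 8.3.3 says when the device is called clinically effective, and 12.0 says in which order hypotheses are tested. Both can be followed as written.

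**2. The plan's own figure, overall type I error 0.05.** Inputs from SAP 12.0: three tests in fixed order, each two-sided at 5%, each reached only if the one before is rejected. Let k be the first true null hypothesis in the order. Any false rejection requires that k be rejected, so

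P(at least one false rejection) ≤ P(reject k) ≤ 0.05.

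The stated 0.05 is reproduced. The argument needs only that each test is valid at its level, so it does not depend on whether Fisher's test or the multiple-imputation analysis is used for the primary endpoint. For contrast, three independent 5% tests without the sequence would give 1 − 0.95³ = 0.143.

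**3. Would adding the 60% condition improve error control?** The stricter gate is a subset of the existing one, so the bound remains 0.05. With equal true rates in both arms (grid from 1% to 99%, Fisher's test, complete data), the largest chance that the gate opens falls from 0.0443 to 0.0235 at 90:45 and from 0.0436 to 0.0239 at 114:57. All four values are already below 0.05.

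**4. When the two rules differ.** Sizes are from the Protocol synopsis: 114:57 randomized and "135 evaluable participants (90 treatment group, 45 control group) at the Month 3 primary timepoint". Reaching 60% takes 0.60 × 90 = 54 responders, or 0.60 × 114 = 68.4, hence 69. Boundary cases with Fisher's test, two-sided:

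| Treatment | Control | p | 60% met? |
|---|---|---|---|
| 53/90 (58.9%) | 18/45 (40.0%) | 0.045 | no |
| 53/90 (58.9%) | 19/45 (42.2%) | 0.099 | no |
| 34/90 (37.8%) | 9/45 (20.0%) | 0.0495 | no |
| 68/114 (59.6%) | 24/57 (42.1%) | 0.035 | no |

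So the mismatch is possible. Its probability is the sum of Binomial(n₁, Pv) × Binomial(n₂, Pc) over outcomes with p ≤ 0.05, treated rate above control and treated rate below 60%. The planning rates are not legible in the public SAP, so all true rates below are assumptions. Ranges are over control rates of 10% to 40%:

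| True treated rate | 90:45 | 114:57 |
|---|---|---|
| 60% | 0.17 to 0.45 | 0.24 to 0.51 |
| 65% | 0.06 to 0.14 | 0.07 to 0.14 |
| 70% | 0.008 to 0.016 | 0.007 to 0.012 |
| 75% | at most 0.0006 | at most 0.0002 |

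**5. What follows when they differ.** Suppose 53/90 against 18/45. H0 is rejected, and the 60% criterion is missed. Under 8.3.3 the device is not declared clinically effective. Under 12.0 FACE-Q Satisfaction with Facial Appearance is tested at 5%. No FACE-Q result can reverse the first conclusion, because 8.3.3 does not refer to FACE-Q. Following the SAP literally gives one answer to each question.

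**6. The price of the stricter gate.** With true rates assumed at 60% treated and 20% control, the chance of reaching the FACE-Q tests is:

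| Sizes | Gate as written | Gate with 60% added |
|---|---|---|
| 90:45 | 0.996 | 0.546 |
| 114:57 | 0.999 | 0.495 |

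**The case for a change.** The best case for a change is about interpretation. SAP 12.0 separates inferential endpoints (FACE-Q) from descriptive ones (GAIS) but says nothing specific about FACE-Q when superiority is shown and 60% is missed. The FACE-Q test is a within-group comparison in participants who know their treatment, so a significant change is quite possible in just that case. A reader might take it as support for a device that failed its own rule. One sentence in Section 12.0 would close the gap without touching alpha or sample size. Section 12.0 also omits the direction condition that 8.3.3 adds to the two-sided p-value.

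The facts in this stand: the two rules are not identical, and the case can occur if the true treated rate is about 65% or lower. The inference does not. The status of FACE-Q is fixed in advance by the text: if H0 is rejected, it is formally tested. A sponsor may reasonably gate on the tested hypothesis alone, and the stricter gate carries the loss shown in step 6. The limits of an unblinded within-group comparison are the same under either gate. The missing direction condition does not affect the error bound either, and rejection in favour of control is very improbable at any rates where treatment works: at 90:45 with 55% against 30%, the probability of any rejection and of rejection in favour of treatment are both 0.78.

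Parts of the SAP (Sections 2.4, 8.3.2 and 11) are not readable, so further wording on this point may exist. The conclusion does not need it.

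**Conclusion.** The concern does not hold. The gate in SAP 12.0 and the success rule in SAP 8.3.3 are different but compatible, and the term used in the gate has one possible meaning. The sequence controls familywise error at 0.05 as stated, and missing 60% still prevents a conclusion of clinical effectiveness. Adding the 60% criterion to the gate is a preference on which statisticians may differ, with a real cost near a 60% treated rate and almost no effect from about 70% up (probability of a difference at most 0.016 at 70% and at most 0.0006 at 75%).

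The probabilities rest on assumed true rates, complete data and Fisher's test. With 171 randomized and 135 evaluable planned, missing data are expected, and the primary analysis would then use multiple imputation in the mITT population, so they are indicative only. The error-control argument rests on none of these assumptions beyond each test holding its own 5% level.

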13.0 Version History

SAP Version History Summary			
SAP Version	Approval Date	Change	Rationale
1	27-Aug-2020	Not Applicable	Original version
2	23-June-2021	Added Interim analysis	Per protocol amendment 2
		Added Appendix C	Per filler study standard
		Writing format change	Per AbbVie SAP template
3	22-September-2021	FACE-Q Satisfaction with Temple Scale update	Appendix F-2, per FACE-Q developer validation report
		Interim efficacy analysis includes visits up to Month 6	Section 11, Adding clarification.
		Volume change of each temple will be summarized by each side (left temple, right temple) as assessed by 3D imaging.	Section 8.5, to be consistent with injection volume data collected by each temple.

Appendix A. Protocol Deviations

Significant protocol deviations will be identified. Unique participants reporting significant protocol deviations will be summarized in total and by treatment group for all randomized or treated participants as described in Table 12. If there are participants who are mistreated, tabulate participants as randomized.

A data listing of significant protocol deviations will be provided. Also, a listing of visits and variables affected by COVID-19 will be included, even if there is no associated significant protocol deviation.

Table 12. Protocol Deviation Summary

Endpoint	Description	Timing	Methodology
Significant protocol deviations	Number (%) of participants with significant protocol deviation will be summarized (All randomized)	During study period	Frequency counts and percentages

Appendix B. Definition of Adverse Events of Special Interest

Refer to Section 9.2.3.

Appendix C. Changes to Protocol-planned Analysis

The subgroup analysis during the control period by volume injected (less than median vs. median or greater) will be only performed for treatment group and will not be done for control group. Volume injected does not apply to control participants during control period.

Appendix D. List of Abbreviations

Abbreviation	Definition
3D	3-dimensional
AE	adverse event
AESI	adverse event of special interest
AO	As Observed
ATHS	Allergan Temple Hollowing Scale
CI	Confidence Interval
CP	Control Period
EI	Evaluating Investigator
FCS	Fully Conditional Specification
GAIS	Global Aesthetic Improvement Scale
ISR	injection site response
MI	Multiple Imputation
mITT	modified intent-to-treat
MedDRA	Medical Dictionary for Regulatory Activities
MI	Multiple Imputation
MP	Maintenance Treatment Period
NRI	Non-Responder Imputation
OPE	Observed Primary Endpoint
PCP	Post-control Period
PP	per-protocol
PT	prefer term
SAE	serious adverse event
SAP	Statistical Analysis Plan
SD	standard deviation
SOC	system organ class
TEAE	treatment-emergent adverse event
TESAE	treatment-emergent serious adverse event
TI	Treating Investigator
TP	Treatment Period
VMT	VOLUMA XC Maintenance Treatment

Abbreviation	Definition
VT	VOLUMA XC Treated
WHO	World Health Organization

Appendix E. Changes to Protocol-planned Analyses

Not applicable.

Appendix F. Scales and Scoring Algorithms

F-1. FACE-Q Satisfaction with Facial Appearance questionnaire

FACE-Q SATISFACTION WITH FACIAL APPEARANCE

	Very Dissatisfied	Somewhat Dissatisfied	Somewhat Satisfied	Very Satisfied
a. How symmetric your face looks?	1	2	3	4
b. How balanced your face looks?	1	2	3	4
c. How well-proportioned your face looks?	1	2	3	4
d. How your face looks at the end of day?	1	2	3	4
e. How fresh your face looks?	1	2	3	4
f. How rested your face looks?	1	2	3	4
g. How your profile (side view) looks?	1	2	3	4
h. How your face looks in photos?	1	2	3	4
i. How your face looks when first wake up?	1	2	3	4
j. How your face looks under bright lights?	1	2	3	4

**FACE-Q SATISFACTION WITH FACIAL APPEARANCE CONVERSION
TABLE**

Instructions: Ensure the data are rescored as follows: "Very Satisfied" = 4; "Somewhat Satisfied" = 3; "Somewhat Dissatisfied" = 2; "Very Dissatisfied" = 1. Higher scores reflect a better outcome. If 1 to 5 of a participant's 10 item scores were missing, the non-missing sum was prorated to a 10-item sum and rounded to the nearest integer. If 6 or more of the 10 item scores were missing, the sum was set to missing. Use the Conversion Table below to convert the raw summed scale score into a score from 0 (worst) to 100 (best).

SUM SCORE	EQUIVALENT RASCH TRANSFORMED SCORE (0-100)
10	0
11	11
12	16
13	20
14	23
15	26
16	29
17	31
18	33
19	35
20	38
21	40
22	42
23	44
24	46
25	48
26	51
27	53
28	55
29	58
30	61
31	64
32	66
33	69
34	72
35	76
36	79
37	82
38	87
39	92
40	100

F-2. FACE-Q Satisfaction with Temples questionnaire

FACE-Q SATISFACTION WITH TEMPLES

	Very Dissatisfied	Somewhat Dissatisfied	Somewhat Satisfied	Very Satisfied	Remark
1. How Well Temples Match Each Other	1	2	3	4	Removed
2. How Full Temples Look	1	2	3	4	
3. The Shape Of Temples	1	2	3	4	
4. How Temples Look In Mirror	1	2	3	4	
5. How Temples Look From The Side	1	2	3	4	
6. How Temples Look Slightly To Side	1	2	3	4	
7. How Temples Look In Photos	1	2	3	4	
8. How Temples Look Under Light	1	2	3	4	
9. Smooth Skin In Temple Area Looks	1	2	3	4	Removed
10. How Symmetric Temples Look	1	2	3	4	Removed
11. Temples Compliment Shape Of Face	1	2	3	4	
12. The Age Temples Make You Look	1	2	3	4	
13. Compared With Other Ppl Your Age	1	2	3	4	
14. How Well Temples Fit With Face	1	2	3	4	
15. The Contour Of Temples	1	2	3	4	Removed
16. How Youthful Temples Make You	1	2	3	4	

FACE-Q SATISFACTION WITH TEMPLES CONVERSION TABLE

Instructions: Ensure the data are scored as follows: "Very Satisfied" = 4; "Somewhat Satisfied" = 3; "Somewhat Dissatisfied" = 2; "Very Dissatisfied" = 1. Higher scores reflect a better outcome.

At the start of this study, 16 items were included in the FACE-Q Satisfaction with Temple Scale and data were collected throughout the study. Based on the result of validation analysis conducted using the baseline data of this study, items 1, 9, 10, 15 were excluded from the scale due to misfit to the Rasch model. The final analysis for this study will include 12 items (i.e., item 2, 3, 4, 5, 6, 7, 8, 11, 12, 13, 14, 16).

The sum of the 12 items will be calculated and converted into an overall score (also known as the Rasch-transformed score) ranging from 0 (worst) to 100 (best). If the number of missing items (which includes selection of more than 1 response for an item, a response of non-applicable (N/A) or skipping a question) is less than 50% of all the items (i.e., at least 7 items have been answered) then insert the unrounded mean of the completed items into the total sum score. Otherwise, the overall score will be missing. The summed score including the imputation of missing items is rounded to the nearest integer and converted to the Rasch-transformed score using the below conversion table.

SUM SCORE	EQUIVALENT RASCH TRANSFORMED SCORE (0-100)
12	0
13	10
14	14
15	16
16	18
17	21
18	23
19	24
20	27
21	29
22	31
23	33
24	36
25	38
26	41
27	43
28	45
29	47
30	49
31	50
32	52
33	54
34	57
35	59
36	62
37	65
38	68
39	71
40	73
41	76
42	79
43	81
44	84
45	87
46	90
47	95
48	100

F-3. Jaw Functional Limitation Scale (JFLS) and Scoring Algorithm

Description

The JFLS was initially developed as an 8-item global scale for overall functional limitation of the masticatory system; based on the resultant items and supporting psychometric data, the instrument was re-developed in order to expand measured constructs to also include masticatory limitation, vertical mobility limitation, and verbal and non-verbal communication limitation, comprised within a 20-item instrument that also retained the items for the short global scale. Consequently, the full instrument could be used at baseline, from which all three subscales as well as the global score could be derived, and the short instrument could be used at follow-up, from which the global score could be derived; measurement congruence across time for a global score would be retained in addition to having subscale scores at baseline. Alternatively, one research group could use the short form and another group could use the long form, and the subscale scores would have measurement congruence across the two settings due to the very high reliability of the global score, whether derived from the full instrument or from the short instrument.

The 20 items are listed below. The score for each item is 0 to 10 with 0 being no limitation and 10 being severe limitation.

1. Chew tough food
2. Chew hard bread
3. Chew chicken
4. Chew crackers
5. Chew soft food
6. Eat soft food requiring no chewing
7. Open wide enough to bite from apple
8. Open wide enough to bite into a sandwich

9. Open wide enough to talk
10. Open wide enough to drink from a cup
11. Swallow
12. Yawn
13. Talk
14. Sing
15. Putting on a happy face
16. Putting on an angry face
17. Frown
18. Kiss
19. Smile
20. Laugh

Scoring

A single global score of "jaw functional limitation" can be computed as the mean of the available items.

Subscale scores for each type of functional limitation are computed, as follows:

- *Mastication*: mean of items 1-6.
- *Mobility*: mean of items 7-10.
- *Verbal and non-verbal communication*: mean of items 13-20.

A second type of global score can be obtained from the long form by computing the mean of the 3 subscale scores, as computed above. Note that all 3 subscale scores must be present in order to compute the global score in this manner.

Alternative scoring can be achieved through the use of Rasch software, but this is not further described in this manual.

Missing data

For the JFLS-20, scores can be computed based on no more than the following number of items with missing response: short form, 2 items missing allowed; mastication, 2 items missing allowed; mobility, 1 item missing allowed; and communication, 2 items missing allowed. For the JFLS-8, no more than 2 items may be missing. Computation of a score with missing items is adjusted by dividing by number of items present.

Interpretation

Norms have not yet been established for this instrument. Based on comparison of individuals who were lifetime negative for TMD to those with chronic TMD, observed scores were as follows:

Scale	No lifetime TMD		Chronic TMD	
	Mean	SE	Mean	SE
Mastication limitation	0.28	0.02	2.22	0.13
Mobility limitation	0.18	0.02	2.22	0.13
Verbal and Emotional Expression Limitation	0.14	0.02	0.72	0.10
Global	0.16	0.02	1.74	0.11

References

[REDACTED]

[REDACTED]

[REDACTED]

[REDACTED]

[REDACTED]

[REDACTED]

[REDACTED]

[REDACTED]

